12.1 Power calculation

A Bayesian approach has been used to calculate the sample size. The Bayesian approach is based on combining a prior distribution for the treatment effect with the result of the trial (which represents here the likelihood). The prior distribution for the effect of Tecfidera vs. placebo was built using the data from DEFINE and CONFIRM trials in RRMS.

12.1.1 Parameter estimates for the rate of events in the RIS cohort in a Bayesian framework

The parameters for the expected treatment effect of a 50% reduction in the risk of the first clinical event are $HR=0.50$ (i.e. $\log HR=-0.69$). A SD for $\log HR$ is set to 2.2 to get a power of 80% to detect a 50% reduction in the hazard of events with 80 patients per arm (original design). This base scenario is set in order to use the same assumptions done as for the original calculations.

Several scenarios were considered to allow a sensitivity analysis for the power calculations.

12.1.2 Parameters for the prior distribution – Scenario 1

The 2 arms treated with Tecfidera are pooled together (i.e. same efficacy)
Patients from DEFINE and CONFIRM are classified as “early RRMS” if they had:

- No previous treatment
- Less than 5 years from disease onset
- EDSS≤1.5

| | Placebo | Tecfidera | Total |
|-------|---------|-----------|-------|
| RRMS | 703 | 1372 | 2075 |
| Early | 68 | 157 | 225 |
| Total | 771 | 1529 | 2300 |

225 patients are classified as Early in the 2 trials merged.

Treatment effect in the “Early” group ($HR=0.24$, risk reduction=76%) $\log HR=-1.45$; $SE=0.31$.
Treatment effect in the rest of RRMS ($HR=0.59$, risk reduction 41%)

The parameters of the prior distribution, according to the Tecfidera effect in early RRMS in the DEFINE+CONFIRM studies, are: mean=-1.45, SD=0.31.

12.1.3 Parameters for the prior distribution – Scenario 2

The 2 arms treated with Tecfidera are pooled together (i.e. same efficacy)
We take the Tecfidera effect form the merged trials: $HR=0.58$, risk reduction=42%; $\log HR=-0.548$; $SE=0.073$.

The parameters of the prior distribution, according to the Tecfidera effect all the patients included in the DEFINE+CONFIRM studies, are: mean=-0.548, SD=0.073.

12.1.4 Parameters for the prior distribution – Scenario 3

The 2 arms treated with Tecfidera are pooled together (i.e. same efficacy)
We take the Tecfidera effect from the merged trials: HR=0.58, risk reduction=42%

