We assume the treatment effect on the RIS cohort to be reduced by 20% since there is a portion of RIS that are not subclinical MS.

HR=0.58*1.20 =0.70

logHR=-0.36

mean=-0.36, SD=0.073.

12.1.5 Parameters for the prior distribution – Scenario 4

The 2 arms treated with Tecfidera are pooled together (i.e. same efficacy)
We take the Tecfidera effect from the merged trials: HR=0.58, risk reduction=42%; SE=0.073

We assume the treatment effect on the RIS cohort to be reduced by 30% since there is a portion of RIS that are not subclinical MS.

HR=0.58*1.30 =0.75; logHR=-0.282; mean=-0.282, SD=0.073

We report here the different power estimates for a sample size of 80 RIS patients (40 per arm) according to the 4 scenarios and 4 different assumptions on SD (representing those observed multiplied by 2, 3, 4 and 5).

| | Prior HR | Parameters for the prior | SD | | | |
|--|-----------------|----------------------------------|------|--------|--------|-----|
| | | | x2 | x3 | x4 | x5 |
| Scenario 1 (early RRMS, subgroup of the trials) | HR=0.235 | Prior mu=-1.45, SD=0.31 | 86% | 70% | 63% | 9% |
| Scenario 2 (all RRMS in the trials) | HR=0.58 | Prior mu= -0.548, SD=0.07 | 100% | 99.60% | 91.30% | 80% |
| Scenario 3 (all RRMS with an effect diluted by 20%) | HR=0.70 | Prior mu= -0.362, SD=0.07 | 99% | 86% | 70% | 61% |
| Scenario 4 (all RRMS with an effect diluted by 30%) | HR=0.75 | Prior mu= -0.282, SD=0.07 | 96% | 67% | 56% | 49% |

Overall, the power analysis shows that the projected sample size of 80 patients should result in adequate power for the majority of scenarios considered.

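### Scenarios 3 and 4 are described as a smaller effect in RIS, but the printed powers fit a true HR of 0.50 with only the prior diluted, and the factors 1.20 and 1.30 are not cuts of 20% and 30%

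*Protocol*

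**What the plan says.** Section 12.1.1 of the protocol sets the base case as an "expected treatment effect of a 50% reduction in the risk of the first clinical event", that is HR 0.50. It sets the SD of the logHR at 2.2 so that 80 patients per arm give 80% power. It then says: "Several scenarios were considered to allow a sensitivity analysis for the power calculations".

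Sections 12.1.4 and 12.1.5 start from HR 0.58 (risk reduction 42%) in the merged RRMS trials. Scenario 3 reads "We assume the treatment effect on the RIS cohort to be reduced by 20" per cent, computed as "HR=0.58*1.20 =0.70". Scenario 4 reads "We assume the treatment effect on the RIS cohort to be reduced by 30" per cent, computed as "HR=0.58*1.30 =0.75; logHR=-0.282; mean=-0.282, SD=0.073". The reason given concerns the trial population: part of RIS is not subclinical MS.

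The power table (80 patients, 40 per arm) labels the last row "Scenario 4 (all RRMS with an effect diluted by 30" per cent, and the Scenario 3 row likewise with 20%. It states no true HR and no success rule. The section concludes that 80 patients "should result in adequate power for the majority of scenarios considered".

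**The concern.** The two sentences and the row labels speak of the effect in the RIS cohort, so a reader may take the Scenario 3 and 4 rows as the chance of success if the drug works less well in RIS than in RRMS. If the powers in fact assume HR 0.50, they answer another question: how much a more pessimistic prior costs when the drug works as well as hoped. Section 5.3 refers to section 12 for the sample-size justification, so the table should show which question it answers.

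The dilution step is a second, separate matter. Raising an HR by 20% or 30% is not the same as reducing an effect by 20% or 30%.

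**Working it through.** **Inputs.** Base HR 0.50 (logHR −0.693) and SD 2.2 come from 12.1.1. The 40 per arm, the prior means −1.45, −0.548, −0.362 and −0.282, the prior SDs 0.31 and 0.07, and the multipliers 2 to 5 come from the power table. The text gives SD 0.073 where the table has 0.07, so recalculated results are shown for both. The success rule is assumed: the posterior 95% interval excludes HR 1 (z = 1.96).

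**Calibration of the rule.** With 80 per arm and no prior, SE = 2.2/√80 = 0.246 and Φ(0.693/0.246 − 1.96) = 80.5%, matching the 80% in 12.1.1. A cut-off of z = 1.645 would give 88.0%, and z = 1.28 would give 93.8%.

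**Model.** The prior is N(μ, s²) and the estimate x is N(θ, SE²), with SE = 2.2/√40 = 0.348. Success requires x below

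x_c = [−1.96·√(1/s² + 1/SE²) − μ/s²] / (1/SE²),

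and power = Φ((x_c − θ)/SE).

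**Example: Scenario 3, SD x3.** s = 0.21, 1/s² = 22.68 and 1/SE² = 8.264. Then x_c = (−1.96 × 5.562 + 22.68 × 0.362)/8.264 = −0.326.
- Truth HR 0.50: Φ((−0.326 + 0.693)/0.348) = 85.4% (printed 86%).
- Truth equal to the diluted effect, logHR −0.362: Φ((−0.326 + 0.362)/0.348) = 54.1%.

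**Reproducing the table with truth HR 0.50 in every row (SD as in the table).**

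| Scenario | Printed x2/x3/x4/x5 (%) | Reproduced (%) |
|---|---|---|
| 1 | 86/70/63/9 | 85.5/68.6/61.2/57.7 |
| 2 | 100/99.6/91.3/80 | 100/99.4/90.3/78.4 |
| 3 | 99/86/70/61 | 99.9/85.4/68.2/60.2 |
| 4 | 96/67/56/49 | 96.0/66.4/54.7/51.2 |

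Fifteen of 16 cells agree within 2.2 points. The exception is the 9% in Scenario 1, which may be a lost digit or an artefact of reading the file.

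**Could each row use its own HR as the truth?** Scenario 1 at HR 0.235 would give 99.9/99.6/99.3/99.1% at z = 1.96, and at least 95% in every cell for any z from 1.28 to 2.576. The printed 86/70/63% rule this out without fixing the success rule.

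**Truth equal to the diluted effect** (the table's prior means, HR 0.696 and 0.754; prior SD 0.073 to 0.07).

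| Scenario | x2 | x3 | x4 | x5 |
|---|---|---|---|---|
| 3 | 97.0–98.7% | 49.5–54.1% | 29.8–31.6% | 23.5–24.4% |
| 4 | 63.6–71.4% | 20.5–22.4% | 13.8–14.4% | 12.3–12.5% |

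Taking the truth as exactly 0.70 and 0.75 moves these by less than 1 point.

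**Dilution step.**
- Risk-reduction scale: 1 − 0.696 = 0.304 and 0.304/0.42 = 0.724, a cut of 28%. 1 − 0.754 = 0.246 and 0.246/0.42 = 0.586, a cut of 41%.
- LogHR scale, against ln 0.58 = −0.545: 1 − 0.362/0.545 = 34% and 1 − 0.282/0.545 = 48%.
- Cuts of 20% and 30% in the risk reduction: 1 − 0.8 × 0.42 = 0.664 and 1 − 0.7 × 0.42 = 0.706.
- Cuts of 20% and 30% in the logHR, from the printed −0.548: exp(−0.438) = 0.645 and exp(−0.384) = 0.681.

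**Direction of the slip.** With truth kept at 0.50 and prior means at 0.664 and 0.706, power rises to 100/90–92/73–75/64–65% (Scenario 3) and about 100/80–83/64–66/58–59% (Scenario 4). The slip alone therefore understates power.

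**The case against.** The protocol largely presents these rows as variations of the prior. The four scenario headings announce parameters of the prior distribution, the table has a column for the prior HR, and 12.1.1 speaks of a sensitivity analysis. Read this way, the diluted effect only explains how the prior mean was obtained, and nobody promised power under a weaker true effect. This stands to a large extent: the exercise is legitimate. It does not rescue the two sentences and row labels, which speak of the effect in the trial population, or the silence on the true HR.

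The true HR and success rule are inferred. Scenarios 3 and 4 alone can be approached otherwise. With each row's own HR as truth, z = 1.28 and SD 0.07, they give 100/92/73/60% and 99/71/51/42%, at most about 7 points from print. Drawing the truth from the prior, with SE 2.2/√80 and z = 1.28, comes closer still for Scenarios 2 to 4. But that second model misses the printed 86/70/63% of Scenario 1 by 12 to 20 points, the first misses them by more, and z = 1.28 does not give the 80% of 12.1.1.

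The dilution scale is not stated, so HR 0.664 and 0.706 are not the only defensible values; the logHR scale gives 0.645 and 0.681. Counts of cells reaching 80% depend on this choice. In Scenarios 3 and 4, 3 of 8 printed cells reach 80%. With truth equal to the diluted effect, the count is 1 of 8 at the protocol's HRs, 2 of 8 at 0.664/0.706, and 3 of 8 at 0.645/0.681 with SD 0.07 (2 of 8 with 0.073). The count is a weak measure; the fall in individual cells at x3 to x5 is the better one.

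A reader might also infer that the trial is underpowered or the whole table inflated. The documents do not support that. Over all 16 cells, 8 printed values reach 80%, against 7 or 8 with each row's own HR as truth, because Scenario 1 would rise to about 99%.

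**Conclusion.** The point holds as a fault of description and arithmetic in the sample-size justification. A true HR of 0.50 in every row is the only reading found that fits the table as a whole and the calibration in 12.1.1. The Scenario 3 and 4 rows therefore show sensitivity to the prior, and the power under the dilution that the text says it assumes appears nowhere. With that dilution as the truth, seven of the eight cells lie about 25 to 45 points below print; only Scenario 3 at x2 stays close. The factors 1.20 and 1.30 match 20% and 30% on neither effect scale, though this slip works against the drug.

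The result rests on the normal model, SE = 2.2/√40, and the inferred true HR and success rule. The figures are powers of the Bayesian rule in section 12.1, not of the log-rank test named for the primary analysis in the synopsis, so they do not show that the primary comparison has too little power.

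**What to change.** - State in section 12.1 the true HR behind the table (apparently 0.50) and the success rule.
- Reword the two sentences on the effect in the RIS cohort, and the two row labels, to say that only the prior mean is diluted.
- Add power for Scenarios 3 and 4 with the true effect equal to the diluted effect.
- Name the scale of the dilution. Then either correct the HRs (0.664 and 0.706 on risk reduction; 0.645 and 0.681 on logHR) or keep 0.70 and 0.75 and relabel the percentages.
- Check the closing sentence on adequate power against the restated table and a stated power target. As printed, 8 of 16 cells reach 80%.
- While recalculating, use one prior SD (0.073 or 0.07) and check the 9% cell against the source.

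The cost is recalculation and rewording. Design, sample size and data collection stay as they are. The downside is that the powers shown for a diluted effect become less favourable, above all at SD x3 to x5, and also for Scenario 4 at x2 if HR 0.75 is kept.

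### The Scenario 1, x5 power in the section 12.1.5 table reads 9%, which does not fit the rest of the table or the section 12.1 inputs; about 58–59% is expected

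*Protocol*

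**What the plan says.** Protocol section 12.1 describes the method in one sentence: "The Bayesian approach is based on combining a prior distribution for the treatment effect with the result of the trial". Section 12.1.1 takes a true hazard ratio of 0.50 (log HR −0.69). It also fixes an SD for log HR; this value "is set to 2.2 to get a power of 80% to detect a 50% reduction in the hazard of events with 80 patients per arm", which was the original design.

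Section 12.1.2 gives the Scenario 1 prior, taken from the early-RRMS subgroup of the two earlier trials; its parameters "are: mean=-1.45, SD=0.31".

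Section 12.1.5 then reports "power estimates for a sample size of 80 RIS patients (40 per arm"), under "4 different assumptions on SD (representing those observed multiplied by 2, 3, 4 and 5"). The Scenario 1 row is "Prior mu=-1.45, SD=0.31 | 86% | 70% | 63% | 9"%. The other rows end, at x5, in 80% (Scenario 2), 61% (Scenario 3) and 49% (Scenario 4). Nothing in the text comments on the 9%.

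**The concern.** The row breaks its own pattern. It falls by 16 points and then by 7, so the steps are shrinking, and then it drops by 54. No other row behaves like this. Scenario 4 has a prior mean much closer to no effect, yet it prints 49% at x5.

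The Scenario 1 prior favours the drug strongly. Widening it should withdraw that support gradually and bring power towards what the trial data give alone, not far below it.

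This table is the only support the protocol displays for 40 per arm, half the original 80 per arm. A wrong entry misinforms anyone using it to judge how sensitive the design is to the prior.

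**Working it through.** **Inputs (Protocol sections 12.1.1 to 12.1.5).** True log HR θ = ln 0.50 = −0.693; SD for log HR 2.2; n = 40 per arm; Scenario 1 prior mean μ = −1.45 and SD 0.31, multiplied by k = 2, 3, 4, 5; Scenarios 2–4 prior means −0.548, −0.362 and −0.282, with SD 0.07 in the table ("Prior mu= -0.548, SD=0.07") and 0.073 in the text.

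**Step 1: recover the unstated parts from the calibration.** Try SE = 2.2/√(n per arm) and a two-sided 5% criterion. With 80 per arm:
- SE = 2.2/√80 = 0.246, and 0.69/0.246 = 2.805.
- Φ(2.805 − 1.96) = 80.1%, which reproduces the protocol's 80%.
- A one-sided 5% criterion (1.645) would give about 88%, which does not.

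So SE = 2.2/√n and z = 1.96 are adopted.

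**Step 2: power formula.** The estimate x is distributed N(θ, SE²). With w₀ = 1/(k·SD)² and w₁ = 1/SE², success means that the posterior mean plus 1.96 posterior SDs is below 0. That is the same as x < c, where

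c = (−1.96·√(w₀ + w₁) − w₀·μ)/w₁, and power = Φ((c − θ)/SE).

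**Step 3: the disputed cell.**
- SE = 2.2/√40 = 0.348 and w₁ = 8.264.
- Prior SD = 5 × 0.31 = 1.55 and w₀ = 0.416.
- √(w₀ + w₁) = 2.946.
- c = (−1.96 × 2.946 + 0.416 × 1.45)/8.264 = −0.626.
- Power = Φ((−0.626 + 0.693)/0.348) = 57.7%.

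With θ = −0.69 the result is 57.3%. A simulation of 1,000,000 draws gives 57.7%.

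**Step 4: the whole table, recomputed (printed), %, with SD 0.07 in Scenarios 2–4.**

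| Scenario | x2 | x3 | x4 | x5 |
|---|---|---|---|---|
| 1 | 85.5 (86) | 68.6 (70) | 61.2 (63) | **57.7 (9)** |
| 2 | 100 (100) | 99.4 (99.6) | 90.3 (91.3) | 78.4 (80) |
| 3 | 99.9 (99) | 85.4 (86) | 68.2 (70) | 60.2 (61) |
| 4 | 96.0 (96) | 66.4 (67) | 54.7 (56) | 51.2 (49) |

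Of the 15 other cells, 14 agree within 2 points and one (Scenario 4, x5) differs by 2.2. With SD 0.073 the largest difference in Scenarios 2–4 is 3.7 points. The Scenario 1 row does not use that SD.

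**Step 5: can 9% be reached?** Widening the Scenario 1 prior further gives 55.7% at x6, 53.8% at x8 and 52.9% at x10. The limit with no prior is Φ(0.693/0.348 − 1.96) = 51.3%. Two ways of forcing a value near 9% both fail:
- The true log HR would have to be about −0.16 instead of −0.69.
- A stricter threshold of z = 3.4 brings x5 down to 10%, but the first three cells then become 28, 15 and 11%, against 86, 70 and 63% printed.

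**The case against.** Four points can be made on the other side.

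- **Possible extraction fault.** The table was read here from machine-extracted text, and one character lost at the end of a row could come from the extraction and not from the protocol. This stands as a caution. The neighbouring cells are intact and nothing marks a gap, but only the issued PDF can settle it.

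- **The method is a reconstruction.** Section 12.1 does not state normality, the standard error formula, the success rule, or whether power is conditional on HR 0.50 or averaged over the prior. A reader might infer that the protocol's documented method has been shown to be incapable of giving 9%. That goes too far: the method was inferred from the calibration and from its fit to the table. The inference is still strong. Other standard errors, a one-sided threshold, averaging over the prior, hybrid classical-Bayesian power, and a true effect equal to the prior mean all fit the table worse, and none puts this cell below 36%.

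- **The fit depends on 0.07.** Agreement within about 2 points needs the table's rounded SD in Scenarios 2–4, and it loosens to 3.7 points with 0.073. This is true, but it does not touch Scenario 1.

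- **Little turns on the cell.** This stands in full. Whether the value is 9, 58 or 59%, it is below 80%. The printed figure errs towards pessimism and cannot create false confidence.

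**Conclusion.** The printed 9% is wrong by about 49 points, if the protocol itself prints it. The expected value is about 58–59%. This rests on the reconstruction above: normal prior and likelihood, SE = 2.2/√40, true HR 0.50, and success when the upper 97.5% posterior limit is below 0.

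A lost leading digit (59%) is the probable cause, since the other printed Scenario 1 values lie 0.5 to 1.8 points above the recomputed ones. That is likely but not established.

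A reader might infer from the printed row that the early-RRMS scenario collapses under a wide prior, or from the correction that the sample size argument changes. The documents support neither. The row behaves like the others. Counting printed cells at 80% or more gives 1 + 4 + 2 + 1 = 8 of 16, before and after the correction. The sample size and the section's closing statement on adequate power are unaffected by it. This is a minor correction to a stated power.

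**What to change.** Check the cell against the issued protocol PDF. If 9% is printed there, check the original power output or re-run the Scenario 1 row, and restate the cell with the verified value, expected to be about 58–59%. The 57.7% derived here should not be inserted directly, because the rest of the row runs slightly above this formula. No other text needs changing on this account, since no passage quotes the table's range. The cost is one table cell, with no change to the design, the sample size or the analysis. If the PDF already shows the right figure, nothing needs to be done.

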3. Incidental anomalies identified on MRI of the brain or spinal cord with the primary reason for the acquired MRI resulting from an evaluation unrelated to multiple sclerosis
4. CNS white matter anomalies meeting the following MRI criteria:
 - a. Ovoid, well-circumscribed, and homogeneous foci with or without involvement of the corpus callosum
 - b. T2-hyperintensities measuring $> 3\text{mm}^2$ and fulfilling 3 of 4 Barkhof-Tintoré criteria for dissemination in space
 - c. CNS anomalies not consistent with a vascular pattern
 - d. Qualitative determination that CNS anomalies have a characteristic appearance of demyelinating lesions
5. MRI anomalies do not account for clinically apparent neurological impairments in patients

Exclusion criteria

1. Women who are pregnant or nursing
2. Incomplete medical history or radiological data
3. History of remitting clinical symptoms consistent with multiple sclerosis lasting > 24 hours prior to CNS imaging revealing anomalies suggestive of multiple sclerosis
4. History of paroxysmal symptoms associated with MS (i.e. Lhermitte's or Uhthoff's phenomena)
5. CNS MRI anomalies are better accounted for by another disease process
6. The subject is unwilling or unable to comply with the requirements of the study protocol

7. Exposure to a disease modifying therapy for multiple sclerosis/RIS within the past 3 months
8. Exposure to high-dose glucocorticosteroid treatment within the past 30 days
9. Participation in other clinical trials involving treatment with a disease-modifying agent

Study design: Prospective, randomized, double-blinded, multi-center

Key data collection:

1. Clinical data
2. Radiologic data
3. Cognitive/Functional Assessments (EDSS, MSFC-expanded)
4. Patient reported surveys
5. Biological samples (CSF, serum DNA and RNA) for future mechanistic studies

Data analysis:

Primary analysis:

- We will evaluate the time from randomization to the first demyelinating event (acute or development of an initial symptom resulting in a progressive clinical course) utilizing Kaplan-Meier survival analyses. Log-rank tests will be used to compare survival data between groups at univariate analysis.

Secondary analyses:

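### The power table that justifies 80 patients describes a Bayesian rule, not the log-rank primary test, which has about 51% to 56% power on the protocol's own inputs

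*Protocol*

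**What the plan says.** Section 12.1 bases the sample size on "combining a prior distribution for the treatment effect with the result of the trial", with priors built from two trials in relapsing-remitting MS. Section 12.1.1 gives the target as HR 0.50. The SD of the log hazard ratio "is set to 2.2 to get a power of 80% to detect a 50% reduction in the hazard of events"; the size used for this calibration is the first design's 80 in each arm. Four prior scenarios follow.

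Section 12.1.5 then halves the sample: "We report here the different power estimates for a sample size of 80 RIS patients (40 per arm) according to the 4 scenarios" and four inflations of the prior SD, "representing those observed multiplied by 2, 3, 4 and 5". The 16 printed powers are:

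| Scenario | x2 | x3 | x4 | x5 |
|---|---|---|---|---|
| 1 | 86% | 70% | 63% | 9% |
| 2 | 100% | 99.6% | 91.3% | 80% |
| 3 | 99% | 86% | 70% | 61% |
| 4 | 96% | 67% | 56% | 49% |

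The conclusion drawn is: "Overall, the power analysis shows that the projected sample size of 80 patients should result in adequate power for the majority of scenarios considered".

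The synopsis, under primary analysis, specifies Kaplan-Meier curves for time from randomization to the first demyelinating event, and adds: "Log-rank tests will be used to compare survival data between groups at univariate analysis". Bayesian Cox models appear only under secondary analyses and in section 12.3, for the predictive value of covariates. Section 5.3 plans approximately 90 subjects and refers to section 12 for the justification.

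**The concern.** The power that matters is that of the test that will decide the trial. The table adds prior information on the treatment effect to the trial data; the log-rank test does not. The protocol itself calibrates its inputs so that 80 per arm gives 80% power, and then keeps those inputs at half that size. Any power above what 40 per arm can give by itself must come from the prior.

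The protocol gives neither the success rule behind the table, nor how often that rule succeeds when the drug has no effect, nor the power without a prior. A reader of section 12 would take a non-significant log-rank result as coming from an adequately powered trial, when the chance of detecting a halved hazard was close to even.

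**Working it through.** **Inputs from the protocol.** Target HR 0.50 and SD 2.2, calibrated to 80% power at 80 per arm (12.1.1); 40 per arm for the table (12.1.5); about 90 subjects, or 45 per arm (5.3). Prior means are -1.45, -0.548, -0.362 and -0.282. Prior SDs are 0.31 for Scenario 1 and, for the others, 0.07 in the table or 0.073 in the text. The level and the success rule are not stated. I infer both from what reproduces the printed figures.

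**Step 1: the calibration.** Take SE = 2.2/√n per arm and power = Φ(0.693/SE - 1.96).
- n = 80: SE = 0.246, and Φ(2.818 - 1.96) = 80.5%. This matches the stated 80% and supports a two-sided 5% level.

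**Step 2: the log-rank test on the same inputs, without a prior.**
- n = 40: SE = 0.348, and Φ(1.993 - 1.96) = **51%**.
- n = 45: SE = 0.328, and Φ(2.114 - 1.96) = **56%**.

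Setting SE² = 4/events, the implied event counts are 4n/2.2², or about 33, 37 and 66 at 40, 45 and 80 per arm.

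**Step 3: the Bayesian table.** Combine a normal prior N(μ, (k·SD)²) with an estimate having SE = 0.348. Declare success if the posterior probability of HR below 1 exceeds 0.975. With w = 1/(k·SD)² and d = 1/SE² = 8.26, success requires an observed log HR below c = [-1.96·√(w + d) - μ·w]/d. The probability of success at a true log HR θ is Φ((c - θ)/SE).

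Example, Scenario 3 at x3 with SD 0.07:
- w = 1/0.21² = 22.68.
- c = (-1.96·√30.94 + 0.362·22.68)/8.26 = -0.326, an observed HR of 0.72.
- Power at HR 0.50 is Φ((-0.326 + 0.693)/0.348) = 85% (printed 86%).
- Success at HR 1 is Φ(-0.326/0.348) = 17%.

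With the table's SD of 0.07, 14 of 16 cells come out within 2 points. The exceptions are Scenario 1 x5 (58% against a printed 9%, probably a lost digit) and Scenario 4 x5 (51.2% against 49%). With SD 0.073 only 8 of 16 do, so 0.07 is the value that fits the table.

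**Step 4: the cells printed at 80% or more (SD 0.07).** The prior-alone column is Φ(|μ|/(k·SD)), the probability of HR below 1 before any patient is enrolled.

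| Cell | Printed | Recomputed power | Success at HR 1 | Success needs observed HR below | Prior alone P(HR<1) |
|---|---|---|---|---|---|
| S1 x2 | 86% | 85.5% | 17.5% | 0.72 | 0.990 |
| S2 x2 | 100% | 100% | 100% | 4.74 | >0.999 |
| S2 x3 | 99.6% | 99.4% | 70% | 1.20 | 0.995 |
| S2 x4 | 91.3% | 90.3% | 24% | 0.79 | just under 0.975 |
| S2 x5 | 80% | 78.4% | 11% | 0.66 | 0.941 |
| S3 x2 | 99% | 99.9% | 88% | 1.50 | 0.995 |
| S3 x3 | 86% | 85.4% | 17% | 0.72 | 0.958 |
| S4 x2 | 96% | 96.0% | 40% | 0.92 | 0.978 |

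The prior alone meets the rule in S1 x2, S2 x2, S2 x3, S3 x2 and S4 x2. With SD 0.073, S4 x2 drops to 0.973 and just misses. The eight cells printed below 80% have 2.5% to 6.6% success at HR 1 and recomputed power of 51% to 69%.

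**Step 5: the count.** As printed, 8 of 16 cells reach 80%: 4 of 4 scenarios at x2, 2 of 4 at x3, and 1 of 4 at x4 and at x5. Recomputed, 7 of 16 do, at either SD, because S2 x5 is 78% (SD 0.07) or 76% (SD 0.073).

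**The case against.** **The count depends on reading.** Section 12.1.5 uses the word scenario for the four rows, and by row all four exceed 80% at x2. Adequate is not defined; at a 70% threshold, 10 of 16 printed cells pass. This stands, so a reader who calls the concluding sentence simply false by count goes too far. But 80% is the only benchmark the protocol names, and by row a majority reaches it only under the narrowest prior.

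**The success rule is inferred.** This also stands. The rule fits 14 of 16 cells, but every success probability at HR 1 depends on it. A looser one-sided 5% rule would raise those probabilities.

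**Error above 2.5% is expected with an informative prior.** A Bayesian design need not hold that level, and operating characteristics may be in an analysis plan not shown here. I accept that their absence from the protocol is not itself an error. The fault is the adequacy conclusion drawn from the table.

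**The high cells do not all ignore the data.** Five of the eight still need an observed HR below 1. S1 x2, for instance, needs one below 0.72 although its prior alone meets the rule. Only S2 x2, S2 x3 and S3 x2 can succeed at some observed HR above 1.

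**The two complaints concern different analyses.** If the log-rank test decides the trial, the 11% to 100% rates do not apply to it. If a Bayesian rule decides, 51% is not its power. That is correct, and it is why the point rests on the mismatch between the two.

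**Conclusion.** The stated adequacy is not a property of the planned primary test. On the protocol's inputs, the log-rank test has about 51% power at 80 subjects and about 56% at 90 for HR 0.50, against the 80% for which those inputs were set at 160. This rests on SD 2.2 and on a two-sided 5% level, which is inferred but reproduces the calibration.

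The table does not support the conclusion firmly even on its own terms. Half of its cells reach 80% as printed and 7 of 16 on recomputation. The cells that do reach it owe much to the prior, with 11% to 100% success at HR 1 (10% to 100% with SD 0.073).

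A reader might infer that the trial itself carries a false-positive rate of that size. The protocol does not support this, because the stated primary test uses no prior. What has to be corrected is the justification of the sample size, not the primary test.

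**What to change.** In section 12.1:

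1. State the power of the log-rank test without a prior as the power of the primary analysis: about 51% at 80 subjects and about 56% at the approximately 90 of section 5.3, with the level given explicitly.
2. Label the 16-cell table as the operating characteristics of a Bayesian rule that is not the primary test. State that rule, and put its success probability at HR 1 beside each power.
3. Replace the concluding sentence with the counts at 80%: 4 of 4 scenarios at x2, 2 of 4 at x3, 1 of 4 at x4 and at x5. Recheck S1 x5 and S2 x5, and use one prior SD (0.07 or 0.073) throughout.
4. Do not rest any claim of adequacy on cells where the prior alone meets the rule.

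This takes recalculation and rewording only. The analysis, sample and conduct are unchanged. The price is a less favourable stated power.
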